9.3.3 Categorisation of Adverse Events

General AE grading scale:

- Grade 1: Transient or mild discomfort (<48 hours); no interference with daily activities; no medical intervention required.
- Grade 2: Mild to moderate interference with daily activity; no or minimal medical intervention required.
- Grade 3: Considerable interference with daily activity; medical intervention required; hospitalization possible.

9.3.4 Causal Relationship Assessment

Causal relationship assessment to drug treatments is required for purposes of reporting AEs. To promote consistency, the following guidelines should be taken into considerations along with good clinical and scientific judgment when determining the relationship of drug treatments to an AE:

Definitely Related: A clinical event, including laboratory test abnormality, occurring in a plausible time relationship to the medication administration, and which cannot be explained by concurrent disease or other drugs or chemicals. The response to withdrawal of the drug should be clinically plausible.

Possibly Related: A clinical event, including laboratory test abnormality, with a reasonable time sequence to the medication administration, but which could also be explained by concurrent disease or other drugs or chemicals. Information on the drug withdrawal may be lacking or unclear.

Unlikely Related: A clinical event, including laboratory test abnormality, with little or no temporal relationship to medication administration, and which other drugs, chemicals or underlying disease provide plausible explanations.

Not Related: A clinical event, including laboratory test abnormality that has no temporal relationship to the medication or has more likely alternative etiology.

9.3.5 Action Taken

Action taken will be defined as:

- None;
- Dose reduced;
- Dosing interrupted;

- Dosing stopped.

9.3.6 Outcome

Outcome will be defined as:

- Resolved;
- Ongoing;
- Lost to follow up.

9.3.7 Coding of Adverse Events

All AEs will be coded using the current version of Medical Dictionary for Regulatory Activities (MedDRA).

9.4 Clinical Laboratory Safety Tests

Sample collection times are included in the schedule of events (see Section 17.0).

9.5 Clinical Laboratory Safety Tests

Sample collection times are included in the schedule of events (see Section 17.0).

Table 3 Laboratory Parameters

Panel	Parameters	
Haematology	Red blood cell count Haemoglobin Haematocrit Platelet count Mean cell volume White blood cell count (total leucocytes) Red cell distribution width-SD Red cell distribution width-CV	Neutrophils (absolute and %) Lymphocytes (absolute and %) Monocytes (absolute and %) Eosinophils (absolute and %) Basophils (absolute and %) Mean corpuscular haemoglobin Mean corpuscular haemoglobin concentration Reticulocyte count
Coagulation	Prothrombin time Activated partial thrombin time	International normalised ratio
Serum biochemistry	Aspartate transaminase Alanine transaminase Alkaline phosphatase Total bilirubin [direct and indirect] Lactate dehydrogenase (LDH) Creatine kinase [a] C-reactive protein	Sodium Potassium Chloride Urea Creatinine Albumin Calcium Phosphate Glucose Bicarbonate Iron studies (serum ferritin, iron and transferrin calculated [% transferrin saturation])
Urinalysis	Leucocytes Protein Bilirubin Urobilinogen Glucose	Ketones Blood pH Nitrite Specific gravity microalbumin creatinine
Urine microscopy	To be performed where clinically indicated	

Serum/urine pregnancy test [b]

[a] Creatine kinase MB fraction will be performed if clinically indicated.

[b] The pregnancy test will be conducted in urine for subjects enrolling from Cohort 17 and 15. The pregnancy test will be conducted on a serum sample at baseline visit for subjects from Cohort 7, 11, 12, 14 or 16 and in urine at the other times.

[c] At the physicians discretion when clinically indicated.

Additional and repeat testing may be performed at the discretion of the Investigator.

Unless otherwise specified all clinical laboratory tests will be performed by Viapath.

Details of all methodology and reference ranges are provided in the Trial Master File.

9.6 Clinical Safety Assessments

Assessment times are included in the schedule of events (see Section 17.0).

Vital Signs

Blood pressure, heart rate, respiration rate and oral temperature will be measured using an automated instrument after the subject has rested comfortably for 2 minutes in the supine position. Additional vital signs may be added for safety of the subjects at the discretion of the Investigator.

12 Lead ECG

Computerised 12-lead ECG recordings will be obtained as a single measurement. Each lead shall be recorded for at least 3 beats at a speed of 25 mm/sec. Subjects should be lying quietly in a fully supine position for at least 5 minutes prior to each 12-lead ECG.

The following parameters will be recorded: rhythm, ventricular rate, PR interval, QRS duration, QT and QTcF.

Medical History

A complete medical history will include evaluation (past or present) of the following: general, head and neck, eyes, ears, nose throat, chest/respiratory, heart/cardiovascular, gastrointestinal/liver, gynecological/urogenital, musculoskeletal/extremities, skin, neurological/psychiatric, endocrine/metabolic, haematologic/lymphatic, allergies/drug sensitivities, past surgeries, substance abuse or any other diseases or disorders.

Physical Examination

Physical examinations will be performed by a physician and will include the examination of the following: general appearance, eyes, ears, nose, throat, chest/respiratory, heart/cardiovascular, gastrointestinal/liver, musculoskeletal/extremities, dermatological/skin, thyroid/neck, lymph nodes, neurological/psychiatric. The physical examinations will include specific surveillance for skin rashes and lymphadenopathy.

In addition a directed physical examination may be conducted if there are any previously identified or new signs or symptoms including any adverse events or diagnoses the subject has experienced since the last visit. Changes from baseline abnormalities should be recorded at each subsequent physical examination. New or worsened abnormalities should be recorded as adverse events if appropriate.

Height and Body Weight

Height will only be measured at baseline visit. The subjects will be required to remove footwear and will wear normal indoor clothing during the measurement of height and weight.

10.0 DATA COLLECTION

Paper CRFs will be produced by Quintiles. Study data including laboratory safety data will be recorded in the CRF by the Investigational Site Staff. Laboratory safety data will be recorded in the CRF only if the lab cannot provide an electronic transfer.

Study data will be recorded on source documents provided by Quintiles when direct data entry into CRFs is inappropriate or impractical. Data from source documents will be transcribed, where necessary, into CRFs by the Investigational Site staff. All source documents will be retained by the investigational site. Photocopies of completed source documents will be provided only if essential (i.e. for regulatory purposes) at the request of the Sponsor.

The CRFs must be kept in order and up-to-date so that they always reflect the latest observations on the enrolled subjects.

Safety laboratory data may be integrated with the consolidated clinical data by Quintiles before database lock.

All records should be kept in conformance to applicable national laws and regulations.

Adverse events will be coded using the current MedDRA thesaurus; concomitant medication will be coded using WHO DD (if required).

CRFs must be completed legibly for each subject enrolled in the study and signed-off by the Investigator.

11.0 EVALUATION OF STUDY DATA

11.1 Evaluation of Pharmacokinetic Parameters

Whole blood and plasma levels of GBT440 as indicated in the schedule of assessments in section 17.

11.2 Evaluation of Pharmacodynamic Measures

11.2.1 Haemolysis markers:

Haemoglobin, unconjugated bilirubin, LDH, absolute and % reticulocyte counts and % dense cells will be measured as indicated in the SOA.

11.2.2 Disease Related Assessments:

Inflammatory markers and exploratory biomarkers related to SCD disease severity will be assessed as indicated in the SOA.

11.3 Evaluation of Safety

The safety evaluation will include blood pressure, pulse rate, body temperature, respiratory rate, ECG parameters, clinical laboratory tests (haematology, serum biochemistry (including erythropoietin), coagulation, urinalysis and urine microscopy) and adverse events.

12.0 STATISTICAL METHODS

Statistical programming and analyses will be performed using established statistical methods. Details of all planned analyses will be specified in a separate statistical analysis plan.

The study data will be reported using summary tables, figures, and data listings. Continuous variables will be summarized using mean, standard deviation (SD), coefficient of variation (CV%, as appropriate), median, minimum, maximum, and, as appropriate, geometric mean. Categorical variables will be summarized by presenting the number (frequency) and percentage in each category.

12.1 Sample Size Determination

This is an extension study following on from GBT440-001. The sample size has therefore not been subject to any statistical considerations.

12.2 Subject Population for Analyses

The PK population will consist of all subjects who receive active study drug and have at least 1 measured concentration at a scheduled PK time point after start of dosing for at least 1 PK analyte. If any subjects are found to be noncompliant with respect to dosing or have incomplete data, protocol violations, or clinical events that affect PK, a decision will be made on a case-by-case basis as to their inclusion in the analysis. Subjects in this population will be used for all PK summaries.

The PD population will consist of all subjects who receive active study drug, and have at least 1 measured value at a scheduled PD time point after start of dosing for at least 1 PD analyte. If any subjects are found to be noncompliant with respect to dosing or have incomplete data, or protocol violations, a decision will be made on a case-by-case basis as to their inclusion in the analysis. Subjects in this population will be used for all PD summaries.

The safety population will include all subjects who receive at least 1 dose of the study drug. Subjects in this population will be used for all demographic and safety summaries.

12.3 Pharmacokinetic Analysis

A listing of PK sample collection times will be provided. Whole blood and plasma levels of GBT440 will be listed and summarised using appropriate descriptive statistics by dose and study day. Where appropriate an estimate of apparent elimination half-life ($t_{1/2}$) will be computed and presented in tabular form with appropriate descriptive statistics

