Subjects from Cohort 15 in the GBT440-001 study who have received GBT440 600 mg per day for two months will continue receiving GBT440 600 mg for a further 4 months in this study or the dose may be increased if the subject has tolerated 600 mg in GBT440-001.

Group 4

Subjects from Cohort 15 in the GBT440-001 study who have received placebo for 2 months will receive GBT440 900 mg per day for 6 months in this study.

Group 5

Subjects from Cohort 7, 11, 12, 14 16 or 17 who received either GBT440 or placebo who are enrolled into this study will receive GBT440 at a dose of 900 mg per day for 6 months.

All Subjects will receive a total of 6 months treatment with GBT440 which will include treatment with GBT440 in the GBT440-001 study for subjects in Cohort 15 or 17. Subjects from Cohort 7, 11, 12, 14, 16 or 17 who received either GBT440 or placebo and are currently off study in GBT440-001 will receive a total of 6 months of treatment with GBT440 in this study..

The dose may be increased by 300 mg increments (1 capsule) every 2 weeks up to maximum of 1500 mg, if in the opinion of the investigator the subject is tolerating the current dose level and might derive further benefit from an increase in dose (e.g. hemolysis measures have improved but not normalized).

A Safety Monitoring Committee (SMC) consisting of the Principal Investigator, Sponsor Medical Monitor, and Independent Safety Physician will have overall responsibility for assessing safety and tolerability. The SMC will review cumulative data at least monthly to determine whether continued dosing may proceed. The responsibilities of the SMC will be described in a separate charter.

Number of Subjects:

Up to 8 SCD subjects from GBT440-001 cohort 17 (900 mg per day), up to 8 SCD subjects from GBT440-001 cohort 15 (600 mg per day), and additional SCD subjects who previously completed GBT440-001 may be enrolled up to a total sample size not exceeding 16 subjects.

Main Criteria for Inclusion:

Subjects with SCD who are currently enrolled in the GBT440-001 study, Cohort 15 or 17.

Subjects with SCD from Cohort 7, 11, 12, 14, 16 or 17 from the GBT440-001 study.

Eligibility may be determined from assessments obtained as part of the GBT440-001 study within 7 days of dosing in this study for subjects in Cohort 15 or 17.

Eligibility must be determined from assessments obtained during baseline visit for subjects who were previously enrolled in Cohorts 7, 11, 12, 14, 16 or 17.

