- Part C consists of a 90-day multiple dose evaluation in subjects with SCD. An amendment has been submitted to extend the dosing period by a further 30 days.

In addition to the above, within Part A, the effect of food (low-fat meal) on the PK profile of GBT440 was evaluated in 1 of the healthy subject cohorts in a crossover design. Subjects in this cohort received 2 doses of GBT440 or placebo; the first dose followed an 8- to 10-hour fast and, following a washout period, the second dose followed a meal.

Part A

Forty-eight (48) subjects have been dosed in 6 single dose cohorts comprised of 40 healthy volunteer subjects (30 received single doses of GBT440 ranging from 100 to 2800 mg and 10 received placebo- Cohorts 1 to 5) and 8 subjects (cohort 7) with SCD (6 received GBT440 1000 mg and 2 received placebo) in this study.

Note: Cohort 6 was not required.

Part B

Sixty two subjects have been dosed in 6 multiple dose cohorts comprised of 24 healthy volunteer subjects (cohorts 8, 9 and 10) dosed for up to 15 days (18 received GBT440 at doses of 300, 600 or 900 mg/day and 6 received placebo), 16 subjects (cohort 11) with SCD dosed for 28 days (12 receiving GBT440 700 mg/day and 4 receiving placebo), 14 subjects (Cohort 12) with SCD dosed for 28 days (GBT440 500 mg/day /placebo), 8 subjects (Cohort 14) with SCD dosed for 28 days (6 receiving GBT440 500 mg twice a day/2 receiving placebo). One subject (cohort 15) with SCD (HbSC and HbS/β⁺thalassemia) has been dosed GBT440 600mg/day/placebo for 28 days. A further 7 subjects (Cohort 15) with SCD (HbSC and HbS/β⁺thalassemia) are to commence dosing with GBT440 600mg/day/placebo for 60 days.

Note: Cohorts 6 and 13 were not required.

Part C

Eight subjects (Cohort 16) with SCD have commenced dosing for 90 days (6 receiving GBT440 700 mg/day and 2 receiving placebo). All eight subjects have completed.

In Cohort 17, 8 subjects with SCD have commenced dosing for up to 118 days receiving GBT440 900 mg/day /placebo). Two of these subjects have completed 90 days of dosing, four of these subjects have completed 118 days of dosing, and two are ongoing. As of 03 August 2016 two subjects from Cohort 17 have enrolled into this study (GBT440-024).

Results

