7.2.1 Subject Inclusion Criteria

1. Male or female subjects with HbSS, HbS/β⁰thalassemia, HbS/β⁺thalassemia, or HbSC aged 18 to 60 years inclusive and >50 kg who have enrolled in cohorts 15 or 17 of the GBT440-001 study and will not experience interruption in dosing for greater than 7 days prior to commencing continuation of dosing in this extension study protocol.
2. Male or female subjects who were enrolled in Cohorts 7, 11, 12, 14, 16 or 17 in the GBT440-001 study (and are currently off-study) are eligible to enroll into this study.
3. Subjects who if female and of child bearing potential, agree to continue to use highly effective methods of contraception prior to enrolment in this study and for 3 months after the last dose of IMP.
4. Subjects whose clinical laboratory test results are not clinically relevant and continue to be acceptable to the Investigator at the final visit of the GBT440-001 study for subjects enrolled in Cohort 15 or 17.
5. Subjects who if male are willing to continue to use barrier methods of contraception, prior to enrolment in this study to 3 months after the last dose of IMP.

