12.4 Pharmacodynamic/Efficacy Analysis

Haemolysis and Disease related assessments will be listed and summarised at each time point using appropriate descriptive statistics.

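### Starting dose largely follows cohort and group membership changes after Days 60 and 120, but the PK and PD summaries name no group, cohort or genotype stratum

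*Combined protocol and SAP*

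**What the plan says.** - **PK.** Section 12.3: "Whole blood and plasma levels of GBT440 will be listed and summarised using appropriate descriptive statistics by dose and study day".
- **PD.** Section 12.4: haemolysis and disease-related measures are listed and "summarised at each time point using appropriate descriptive statistics". No stratum is named.
- **Size.** Section 3.0 allows enrolment "up to a total sample size not exceeding 16 subjects". Section 12.1: "The sample size has therefore not been subject to any statistical considerations".
- **Cohort 15.** Section 5.2.1 gives its genotypes: "A further 7 subjects (Cohort 15) with SCD (HbSC and HbS/β⁺thalassemia" (bracket left open here). No other cohort's genotype is given. Inclusion criterion 1 (section 7.2.1) lists four genotypes jointly for subjects "who have enrolled in cohorts 15 or 17 of the GBT440-001 study".
- **Starting dose.** Group 3 is "Subjects from Cohort 15 in the GBT440-001 study who have received GBT440 600 mg per day for two months" and continues at 600 mg unless the dose is raised. Groups 1, 2 and 5 start at 900 mg. Group 4 (Cohort 15, previously placebo) starts at 900 mg in sections 3.0, 7.1 and 8.6 and in the heading text of Table 5, but at 600 mg in Table 5 footnote d.
- **End of treatment in this study.** Day 60 in Group 1 (Table 4), Day 120 in Group 3 (Table 6), Day 180 in Groups 2, 4 and 5 (Table 5).
- **Further detail.** Section 12.0 leaves the details to a separate statistical analysis plan, whose text was not among the documents reviewed.

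**The concern.** Two features of the design reach the tables if sections 12.3 and 12.4 are carried out as written.

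First, a PK table by dose sets mostly Cohort 15 subjects (600 mg) against mostly other subjects (900 mg). Section 5.1.2 reports that the drug concentrates in red cells at about 150:1 relative to plasma, and section 5.1.3 that it binds haemoglobin specifically. Whole-blood level can therefore depend on a subject's haemoglobin as well as on dose. Section 5.3.1 reasons from blood level and haemoglobin occupancy to titration, so this table is likely to be read closely.

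Second, study day does not mean the same thing in every group. Groups 1 and 3 enter already on drug, while Groups 2, 4 and 5 start drug in this study. Group 1 then drops out of the on-treatment set after Day 60 and Group 3 after Day 120. A mean haemoglobin by visit could fall late in the study, and look like loss of effect, only because its membership changed. Describing the effect on haemolysis biomarkers is a secondary objective (section 6.2), and these descriptive tables are its only planned answer.

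**Working it through.** The plan states no power, effect size or derived sample size, so there is no figure to reproduce. The check counts who is in each cell.

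**Assumptions, none stated in the documents:** 16 enrolled; Cohort 15 contributes between 3 active + 1 placebo and 6 + 2 (the 6:2 split is that of Cohort 14 in section 5.2.1; Cohort 15's own split is not given); 0 to 2 subjects in Group 1; no titration, reduction or dropout; Cohort 15 differs from the others by 1 to 3 g/dL in haemoglobin, and no subject's value changes.

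**1. Starting-dose cells (6 + 2 from Cohort 15, 8 others)**

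| Source for Group 4 | Cohort 15 share at 600 mg | Cohort 15 share at 900 mg |
|---|---|---|
| Main text (900 mg) | 6/6 | 2/(2 + 8) = 20% |
| Table 5 footnote d (600 mg) | 8/8 | 0/8 |

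Under the main text, 5 + 2 gives 2/11 = 18% at 900 mg, 4 + 1 gives 1/12 = 8.3%, and 3 + 1 gives 1/13 = 7.7%. Confounding at the start is strong under the main text and complete under the footnote.

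**2. Months on GBT440 at a given study day, including GBT440-001**

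| Study day | Group 1 | Group 3 | Groups 2, 4, 5 |
|---|---|---|---|
| 60 | 4 + 2 = 6 | 2 + 2 = 4 | 2 |
| 120 | off drug | 2 + 4 = 6 | 4 |
| 180 | off drug | off drug | 6 |

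For Group 5 this counts only dosing in this study.

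**3. Shift in an unstratified mean**

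Share = Cohort 15 subjects on treatment / all subjects on treatment. Shift = (share at Day 150 − share at Day 120) × assumed difference.

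| Cohort 15 | Group 1 | Share, Day 120 | Share, Day 150 | Shift for 1, 2, 3 g/dL |
|---|---|---|---|---|
| 6 + 2 | 0 | 8/16 = 0.500 | 2/10 = 0.200 | −0.30, −0.60, −0.90 |
| 6 + 2 | 2 | 8/14 = 0.571 | 2/8 = 0.250 | −0.32, −0.64, −0.96 |
| 5 + 2 | 0 | 7/16 = 0.438 | 2/11 = 0.182 | −0.26, −0.51, −0.77 |
| 4 + 1 | 0 | 5/16 = 0.312 | 1/12 = 0.083 | −0.23, −0.46, −0.69 |
| 3 + 1 | 0 | 4/16 = 0.250 | 1/13 = 0.077 | −0.17, −0.35, −0.52 |
| 3 + 1 | 2 | 4/14 = 0.286 | 1/11 = 0.091 | −0.19, −0.39, −0.58 |

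The range is 0.17 to 0.96 g/dL. The minus sign assumes that Cohort 15 has the higher haemoglobin; if it were lower, the sign would reverse. The loss of 1 or 2 Group 1 subjects after Day 60 gives a smaller shift the other way, 0.02 to 0.21 g/dL.

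**4. Neighbouring visits.** Group 1's off-drug final visit (Day 88) falls beside the other groups' Day 90. Group 3's off-drug final visit (Day 148) falls beside Day 150 for Groups 2, 4 and 5. A table by nominal visit window could combine them.

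**The case against.** The strongest reply is that this is a descriptive extension study of at most 16 people. No dose comparison or proportionality analysis is planned, individual values are listed, and the separate analysis plan may already present everything by group; the group-specific schedules make that a natural choice. This stands in part. It means that the risk is misreading and that no error rate is affected. It does not remove the gap, because sections 12.3 and 12.4 are the only analysis text reviewed and they name no stratum.

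A reader might also infer three stronger things that the documents do not support.

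- **That 600 mg is given only to subjects with HbSC or HbS/β⁺ thalassemia.** At most this describes planned starting dose. Section 8.3 allows reductions in 300 mg steps, section 8.2 allows restart at a lower dose, and section 3.0 carries over reductions made in GBT440-001, so a subject from another cohort can be at 600 mg. Section 8.2.1 lets Group 3 move up. Since the other cohorts' genotypes are not given, Cohort 15 versus the rest is documented, but a clean genotype contrast is an inference.
- **That section 12.4 specifies pooling.** It is silent on strata.
- **That all PK results are affected alike.** The haemoglobin argument concerns whole blood and does not carry over directly to plasma. The documents give no model linking dose to occupancy by genotype, so no size is put on the PK effect here.

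**Conclusion.** The concern holds as a limit on interpretation. Starting dose is strongly, though not completely, confounded with cohort; the degree depends on which Group 4 dose applies, and the conflicting places must be reconciled. Study day mixes subjects already on drug with subjects starting it, and on-treatment membership changes by design after Days 60 and 120. Under the stated assumptions, an unstratified haemoglobin mean moves by about 0.2 to 1.0 g/dL between Days 120 and 150 with no subject changing. That size rests on assumed enrolment, an assumed split and an assumed haemoglobin difference. The change in membership itself follows from the schedules whenever Groups 1 and 3 are populated. The remedy is cheap and worth making before the analysis plan is final.

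**What to change.** In sections 12.3 and 12.4, or in the separate analysis plan:

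1. Present PK and PD by group (or by Cohort 15 versus other cohorts, or genotype class) and by dose received, with n at each time point.
2. Show PD as within-subject change from the pre-GBT440 baseline. For Groups 1 and 3 take it from GBT440-001, because their Visit 0 is their last treatment day in that study.
3. Follow a fixed set of subjects over each interval: all groups to Day 60; Groups 2, 3, 4 and 5 to Day 120; Groups 2, 4 and 5 to Day 180. Keep off-drug final visits out of on-drug visit windows.
4. State that a 600 versus 900 mg difference in whole-blood level will not be interpreted as a pure dose effect.
5. Reconcile the Group 4 dose between the main text and Table 5 footnote d.

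Before fixing the Day 60 set for haemoglobin, check the schedules. As the tables read here, haematology at Day 60 is marked in Table 6 but not in Tables 4 and 5, although this may be an artefact of text extraction.

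The cost is wording and table layout, with no new data collection in this study. The downside is very small cells: on the 6 + 2 example with Group 4 at 900 mg, Cohort 15 has 6 subjects at 600 mg and 2 at 900 mg, and the other cohorts have 0 and 8. With at most 16 subjects and individual listings already planned, that is acceptable.
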